8. STATISTICAL METHODS AND STATISTICAL ANALYSIS

8.1. Statistical Methods

8.1.1. Analysis of Continuous Data

Summary statistics (number of patients, mean, standard deviation, median, maximum, and minimum) will be calculated.

8.1.2. Analysis of Categorical Data

The frequency (e.g., number of patients) and proportion of each category will be calculated.

8.1.3. Analysis of Binary Data

The frequency and proportion will be calculated. If the confidence interval of proportion is calculated, two-sided 95% confidence interval (exact method) will be calculated.

If the proportion is compared between subgroups, risk ratio and its 95% confidence interval, and risk difference and its 95% confidence interval will be calculated. In addition, risk ratio and its 95% confidence interval will be graphically presented (see Appendix 2). If the number of patients in at least one category compared is \leq 5, the number of patients and proportion will be calculated but risk ratio and its 95% confidence interval, and risk difference and its 95% confidence interval will not be calculated.

8.1.4. Analysis of Period Data (Time to Event Onset)

The median, first quartile, and third quartile by Kaplan-Meier method will be calculated. In addition, Kaplan-Meier plots will be prepared.

8.2. Statistical Analysis

8.2.1. Overview of Patients

• Number of sites by establisher and number of patients

In patients for whom the case report form was collected, the number and proportion of sites by establisher shown below and the number and proportion of patients will be calculated.

- University hospitals
- National hospitals established by the Ministry of Health, Labour and Welfare
- Prefectural and municipal hospitals

- Public organizations
- Hospitals other than the above four established by corporations and individuals
- General practitioners/clinics

In addition, the mean, minimum, and maximum will be calculated for the number of patients per site.

• Dispositions of patients

In patients who completed the study, the number of patients included in the analysis of safety and the number of patients included in the analysis of effectiveness will be tabulated. In addition, the number of patients excluded from the analysis of safety and effectiveness and the number of patients by reason for exclusion will be tabulated.

• Listing of discontinuations and dropouts

In the safety analysis set, the number and proportion of patients who completed or discontinued treatment will be tabulated by timing (<30 days, \geq 30 to <60 days, \geq 60 to <90 days, \geq 90 to <120 days, \geq 120 to <150 days, \geq 150 to <180 days, \geq 180 days, overall). In addition, the number and proportion of patients by reason for completion and discontinuation will be tabulated. The listing of other reasons for discontinuation will be prepared.

• Listing of excluded patients

The listing of patients excluded from the analysis of safety and effectiveness and reasons for exclusion will be prepared.

8.2.2. Patient Background and Treatment History of Vfend

• Patient background

In the safety analysis set and effectiveness analysis set, the following patient background factors will be tabulated in accordance with Section 8.1.

- Sex [male, female]
- Age (years; continuous)
- Age [<15 years, ≥ 15 to <65 years, ≥ 65 years]
- Age (children 1) [newborns (<1 month after birth), infants (≥1 month to <1 year), younger children (≥1 to <7 years), children (≥7 to <15 years)]
- Age (children 2) [≤ 2 years, ≥ 2 to ≤ 15 years]
- Age (adults) [≥15 to <20 years, ≥20 to <40 years, ≥40 to <65 years, ≥65 to <70 years, ≥70 to <75 years, ≥75 years]
- Hospitalized status [inpatient, outpatient]
- Body weight (kg; continuous)
- Objective of treatment [primary prophylaxis (patients without history of fungal infection), secondary prophylaxis (patients with history of fungal infection), others]
- Details of other objectives of treatment

- Type of transplantation [autograft, allogeneic full transplantation, allogeneic mini-transplantation]
- Source of transplantation [bone marrow, cord blood, peripheral stem cell]
- Occurrence of GVHD (graft versus host disease) [absent, present]
- Indication for transplantation [leukemia, myelodysplastic syndrome, malignant lymphoma, myeloma, others]
- Severity of indication for transplantation [mild, moderate, severe]
- Hepatic dysfunction [absent, present, unknown]
- Severity of hepatic dysfunction [mild, moderate, severe, unknown]
- Renal dysfunction [absent, present, unknown]
- Severity of renal dysfunction [mild, moderate, severe, unknown]
- Past medical history [absent, present]
- Concurrent illness [absent, present]
- Concurrent congenital severe immunodeficiency [absent, present]
- White blood cell count before administration [$<3000/\mu$ L, $\geq 3000/\mu$ L]
- Neutrophil count before administration [$<500/\mu$ L, $\geq 500/\mu$ L]
- Concomitant use of immunosuppressants (other than steroids) [absent, present]
- Concomitant use of steroids [absent, present]
- Concomitant use of steroids or immunosuppressants other than steroids [absent, present]
- Use of contraindicated concomitant medications [absent, present]
- Use of concomitant medications requiring precautions for coadministration [absent, present]
- Concomitant use of other antifungal agents [absent, present]
- Concomitant use of broad-spectrum antibiotics [absent, present]
- Prior treatment (antifungal agents administered for prophylaxis of invasive fungal infections)
 [absent, present]

In the safety analysis set, the number and proportion of the following patients will be tabulated by System Organ Class (SOC) and Preferred Term (PT) of MedDRA.

- Past medical history
- Concurrent illness
- Concurrent congenital severe immunodeficiency

In the safety analysis set and effectiveness analysis set, the number and proportion of the following patients will be tabulated.

- Contraindicated concomitant medications
- Concomitant medications requiring precautions for coadministration
- Concomitant immunosuppressants
- Concomitantly used other antifungal agents
- Prior treatment (antifungal agents for prophylaxis of invasive fungal infections)
- Reasons for discontinuation of prior treatment (antifungal agents for prophylaxis of invasive fungal infections)
- Presence/absence of pregnancy

In the safety analysis set (women), the number of patients by pregnancy status will be calculated.

• Status of treatment of Vfend

In the safety analysis set, the following status of treatment of Vfend will be tabulated.

- Treatment period [≥1 to <30 days, ≥30 to <60 days, ≥60 to <90 days, ≥90 to <120 days, ≥120 to<150 days, ≥150 to <180 days, ≥180 days]
- Long-term treatment [<180 days, $\geq 180 \text{ days}$]
- Treatment period (days; continuous)
- Dose on the first day (mg; continuous)
- Mean maintenance dose (mg; continuous)
- Dose on the first day (mg/kg; continuous)
- Mean maintenance dose (mg/kg; continuous)
- Overdose³ [absent, present]

The treatment period is from the initial day of administration in this study to the last confirmed day of administration, including the period during which Vfend is suspended.

Tabulation by age (1) [<15 years, \geq 15 years] will be performed in the same manner as above.

8.2.3. Safety Analysis

Adverse drug reactions and adverse events observed during the observation period (from the day of initiation of Vfend treatment to the day of completion of treatment) + follow-up period (28 days*) will be tabulated. If the duration of the observation period + follow-up period is beyond October 31, 2018, events observed by October 31, 2018 will be tabulated. All events reported in this study will be included in listings.

*: The duration of the follow-up period in this study was set at 28 days because a 30-day follow-up period was provided in a clinical study and the period of collection of adverse events using NIS AE Report Form in this study is up to 28 days after the day of completion of treatment.

8.2.3.1. Adverse Drug Reactions

• All adverse drug reactions

The number and proportion of patients with adverse drug reactions will be tabulated by SOC and PT.

• Serious adverse drug reactions

³: The initial dose and the mean dose (mean maintenance dose) for each of injection and oral agent on and after Day 2 will be calculated for each patient, and administration at doses exceeding the upper limit of the dosage regimen of Vfend or the maximum dose will be considered as overdose.

The number and proportion of patients with serious adverse drug reactions will be tabulated by SOC and PT.

• Details of adverse drug reactions

The number and proportion of patients with adverse drug reactions will be tabulated by SOC and PT for each of the following items and factors.

- Age (1) [\leq 15 years, \geq 15 years]
- Age (2) [≤ 65 years, ≥ 65 years]
- Hepatic dysfunction [absent, present, unknown]
- Renal dysfunction [absent, present, unknown]
- Long-term treatment [<180 days, ≥ 180 days]
- Seriousness [serious, non-serious]
- Expected/unexpected [Expected, unexpected]
- Change in treatment with Vfend [discontinuation, temporarily discontinued, dose reduction, dose increase, no change]
- Outcome [not recovered, recovered with sequela, recovering, resolved/recovered, unknown]

In addition, the number and proportion of patients with serious adverse drug reactions will be tabulated by SOC and PT for each of the following items and factors.

- Age (1) [<15 years, ≥ 15 years]
- Age (2) [<65 years, ≥ 65 years]
- Hepatic dysfunction [absent, present, unknown]
- Renal dysfunction [absent, present, unknown]
- Long-term treatment [<180 days, $\geq 180 \text{ days}$]
- Expected/unexpected [Expected, unexpected]
- Change in treatment with Vfend [discontinuation, temporarily discontinued, dose reduction, dose increase, no change]
- Outcome [not recovered, recovered with sequela, recovering, resolved/recovered, unknown]

If the same adverse event (the same PT) occurs more than once in the same patient, it will be handled as follows in the tabulation of the number of patients with events:

- Seriousness: If both serious and non-serious events are reported, "serious" will be adopted.
- Expected/unexpected: If both expected and unexpected events are reported, "unexpected" will be adopted.
- Number of days to onset: The number of days to the first event will be adopted.
- Change in treatment with Vfend: If multiple types of change in treatment with Vfend are reported, one of discontinuation, temporarily discontinued, dose reduction, dose increase or no change, in descending order of precedence, will be adopted.
- Outcome: The outcome of the last occurring event will be used.
- Safety specifications

The number and proportion of patients with events will be tabulated. In addition, the number and proportion of patients with safety specifications by change in treatment with Vfend and outcome will be tabulated by SOC and PT.

• Major investigation items

The number and proportion of patients with major investigation items will be tabulated by SOC and PT. In addition, the number and proportion of patients with major investigation items will be tabulated by SOC and PT for each of the following items.

- Change in treatment with Vfend [discontinuation, temporarily discontinued, dose reduction, dose increase, no change]
- Outcome [not recovered, recovered with sequela, recovering, resolved/recovered, unknown]
- Age (1) [<15 years, ≥ 15 years]

Furthermore, in order to examine the difference between patients who discontinued treatment and those who did not by major investigation item, patients with major investigation items will be tabulated by patient background factor, status of discontinuation/completion, concomitant medication, and status of administration.

• Timing of onset of adverse drug reactions

The number of patients with adverse drug reactions will be tabulated by SOC and PT by timing of initial onset of adverse drug reactions. Categories of timing of onset will be every 30 days. However, if there are many adverse drug reactions that occur at an early stage, the analysis will be performed by subdividing the category of the first 30 days as necessary. Major investigation items will be analyzed in the same manner.

For major investigation items, time to event onset will be summarized for each patient in accordance with Section 8.1.4 with the initial onset of the major investigation item considered as an event. Patients without adverse drug reactions will be right-censored after the observation period + follow-up period (28 days) of this study.

• Relationship between concomitant medications and development of adverse drug reactions

The number and proportion of patients with adverse drug reactions and major investigation items will be tabulated overall and by PT by presence or absence of actually used concomitant medications for each adverse drug reaction and major investigation item to evaluate the relationship of contraindicated concomitant medications, concomitant medications requiring precautions for coadministration, concomitantly used other antifungal agents, and concomitant immunosuppressants with adverse drug reactions considered as major investigation items. However, medications started to be used after the day of the last onset of the event during the observation period + follow-up period (28 days) will be excluded from tabulation.

In addition, the number and proportion of patients with adverse drug reactions and major investigation items will be tabulated by PT by presence or absence of each actually used concomitant medication for

each adverse drug reaction and major investigation item to evaluate the relationship of contraindicated concomitant medications, concomitant medications requiring precautions for coadministration, concomitantly used other antifungal agents, and concomitant immunosuppressants with adverse drug reactions considered as major investigation items. However, medications started to be used after the day of the last onset of the event during the observation period + follow-up period (28 days) will be excluded from tabulation.

• The adverse drug reactions by patients of included/excluded in the safety analysis set

In patients for whom the case report form was collected, the listing of adverse drug reactions in patients excluded from the safety analysis set will be prepared. The number of patients with events will be tabulated by SOC and PT.

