# [ DOSAGE AND ADMINISTRATION ]

<for Intravenous Use>

Adult	Voriconazole is administered by intravenous drip infusion at the dose of 6 mg/kg twice daily on day 1 and 3 mg/kg or 4 mg/kg twice daily from day 2 onward.
Children (Aged 2 to <12 and 12 ≥ whose body weight is less than 50 kg)	9 mg/kg as voriconazole twice daily on day 1 and 8 mg/kg twice daily from day 2 should be given intravenously. Dose may be increased depending on condition of patients or if poorly responded_by 1 mg/kg at a time, and dose in intolerant patients should be reduced by 1 mg/kg at a time.
Children (Aged ≥12 whose body	6 mg/kg as voriconazole twice daily on day 1 and 4 mg/kg twice
weight is 50 kg or more)	daily from day 2 should be given intravenously.

<tablet></tablet>	
Adult (body weight ≥40 kg)	A recommended oral dose of voriconazole is 300 mg twice daily between meals on day 1, and 150 or 200 mg/dose twice daily between meals on day 2 and thereafter. Dose may be increased depending on condition of the patients or if poorly responded; provided that a total daily dosage should not exceed 400 mg/dose twice daily on day 1 and 300 mg/dose twice daily on day 2 and thereafter.
Adult (body weight <40 kg)	A recommended oral dose of voriconazole is 150 mg twice daily between meals on day 1, and 100 mg/dose twice daily between meals on day 2 and thereafter. Dose may be increased from day 2 onward depending on condition of patients or if poorly responded; provided that a total daily dosage should not exceed 150 mg/dose twice daily.
Children (Aged 2 to <12 and ≥12 whose body weight is less than 50 kg)	After the administration of Voriconazole injection, a recommended maintenance oral dose of voriconazole following injection therapy is 9 mg/kg/dose twice daily between meals. Dose may be increased by 1 mg/kg at a time depending on condition of patients or if poorly responded, and dose in intolerant patients should be reduced by 1 mg/kg at a time (unless the dosage was at its maximum 350 mg, in which case, dose should be reduced by 50 mg at a time). A total daily dosage should not exceed 350 mg/dose twice daily.
Children (Aged ≥12 whose body weight is 50 kg or more)	After the administration of Voriconazole injection, a recommended maintenance oral dose of voriconazole following injection therapy is 200 mg/dose twice daily between meals; which may be increased up to 300 mg/dose twice daily depending on condition of patients or if poorly responded.
<dry syrup=""></dry>	

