5.4. Subgroup Analysis

Subgroup analyses of safety and effectiveness will be performed for the following patient background factors and other factors. Levels in parentheses are levels of subgroups, and underlined levels are the reference for calculation of risk ratio and risk difference.

- Sex [male, female]
- Age (1) [<15 years, ≥ 15 years]
- Age (2) [<65 years, ≥65 years)
- Age (children 1) [newborns (<1 month after birth), infants (≥1 month to <1 year), younger children (≥1 to <7 years), children (≥7 to <15 years)]
- Age (children 2) [<2 years, ≥ 2 to <15 years]
- Hospitalized Status [inpatient, outpatient]
- Objective of treatment [primary prophylaxis (patients without history of fungal infection), secondary prophylaxis (patients with history of fungal infection), others]
- Type of transplantation [autograft, allogeneic full transplantation, allogeneic mini-transplantation]
- Source of transplantation [bone marrow, cord blood, peripheral stem cell]
- Occurrence of GVHD (graft versus host disease) [absent, present]
- Indication for transplantation¹ [leukemia, myelodysplastic syndrome, malignant lymphoma, myeloma, others]
- Severity of indication for transplantation [mild, moderate, severe]
- Hepatic dysfunction [absent, present]
- Severity of hepatic dysfunction [mild, moderate, severe]
- Renal dysfunction [absent, present]
- Severity of renal dysfunction [mild, moderate, severe]
- Past medical history [absent, present]
- Concurrent illness [absent, present]
- Congenital severe immunodeficiency² [absent, present]
- White blood cell count before administration [$<3000/\mu$ L, $\geq 3000/\mu$ L]
- Neutrophil count before administration [$<500/\mu$ L, $\geq 500/\mu$ L]
- Concomitant use of broad-spectrum antibiotics [absent, present]
- Use of contraindicated concomitant medications [absent, present]
- Use of concomitant medications requiring precautions for coadministration [absent, present]
- Concomitant use of immunosuppressants (other than steroids) [absent, present]
- Concomitant use of steroids [absent, present]
- Concomitant use of steroids or immunosuppressants other than steroids [absent, present]
- Concomitant use of other antifungal agents [absent, present]
- Prior treatment (antifungal agents administered for prophylaxis of invasive fungal infections)
 [absent, present]
- Long-term treatment [$\leq 180 \text{ days}$, $\geq 180 \text{ days}$]

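### Overdose is judged on the initial dose and a per-route mean from Day 2, so a patient above the label ceiling on many maintenance days can be tabulated as having no overdose

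*SAP*

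**What the plan says.** Overdose is one of the treatment-status items in SAP 8.2.2, tabulated as absent or present in the safety analysis set and again by age under 15 and 15 or over. Its definition is footnote 3, which the extracted text places within 8.2.3.1. Per patient, the footnote calculates "The initial dose and the mean dose (mean maintenance dose) for each of injection and oral agent on and after Day 2". It continues: "administration at doses exceeding the upper limit of the dosage regimen of Vfend or the maximum dose will be considered as overdose".

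The limits come from the dosage section under protocol 7.2.1. For adults of 40 kg or more taking oral drug, "a total daily dosage should not exceed 400 mg/dose twice daily on day 1 and 300 mg/dose twice daily on day 2 and thereafter". For adults under 40 kg, "a total daily dosage should not exceed 150 mg/dose twice daily". For children under 50 kg on oral drug, "A total daily dosage should not exceed 350 mg/dose twice daily". For adult intravenous use the highest regimen dose from Day 2 is 4 mg/kg twice daily.

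Two other parts of SAP 8.2.3.1 bear on the point. Dose reduction and dose increase are coded responses to a reaction; where several are reported, "one of discontinuation, temporarily discontinued, dose reduction, dose increase or no change, in descending order of precedence, will be adopted". Patients with hepatic toxicity or visual events are also tabulated by status of administration, among other things, to compare those who discontinued with those who did not.

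**The concern.** The ceilings limit what may be given on each day from Day 2. A mean over the whole maintenance course answers a different question. Days below the ceiling offset days above it, so the average can be acceptable while the ceiling was broken for weeks. The tabulated overdose count would then be too low.

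The mean also takes in doses given after a reaction. Two patients with the same exposure up to onset can be classified differently because one stopped and the other continued on a lower dose. Protocol 7.3.8 asks how dose differs between patients who could continue and patients who had to stop. If the flag were used there, it would partly reflect the response to the event.

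**Working it through.** The documents state no overdose count or rate, so there is no planned figure to reproduce. The check applies the footnote's rule to assumed dose histories. Doses are mg per dose given twice daily (mg/kg for intravenous), maintenance days run from Day 2, and Day 1 is taken to be within its own limit.

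**1. How many days above the limit can go unflagged.** Let L be the limit from Day 2, H a dose above it and l a lower dose on the remaining days. If a share f of days is at H, the mean is fH + (1 − f)l. The flag stays off while the mean does not exceed L, that is while f ≤ (L − l)/(H − l).

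| Group and route (L) | l / H (assumed) | Largest unflagged share |
|---|---|---|
| Adult oral, 40 kg or more (300 mg) | 200 / 400 | 100/200 = 50% |
| | 150 / 350 | 150/200 = 75% |
| | 250 / 450 | 50/200 = 25% |
| Adult oral, under 40 kg (150 mg) | 100 / 200 | 50/100 = 50% |
| | 100 / 300 | 50/200 = 25% |
| Child oral, under 50 kg (350 mg) | 300 / 400 | 50/100 = 50% |
| | 250 / 400 | 100/150 = 67% |
| Adult intravenous (4 mg/kg) | 3 / 6 | 1/3 = 33% |

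If the other days are at the limit itself, l = L and the share is 0%. Using daily totals for oral dosing doubles every term and leaves the shares unchanged.

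**2. How later dosing changes the flag** (adult oral, 40 kg or more, limit 300 mg).

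- 14 days at 400 mg, then stopped: mean 400 mg, present.
- 14 days at 400 mg, then 15 days at 200 mg: (14 × 400 + 15 × 200)/29 = 8600/29 = 296.6 mg, absent, with 14 of 29 days (48%) above the limit.
- 14 days at 200 mg, then raised to 400 mg for 15 days after a reaction: (14 × 200 + 15 × 400)/29 = 8800/29 = 303.4 mg, present, with no dose above the limit before onset.

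The first two patients have the same exposure up to day 14 of maintenance. The third shows that the flag can move the other way.

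**3. Suspended days.** SAP 8.2.2 counts suspended days in the treatment period but does not say whether they enter the mean dose. If they entered as zero, 20 days at 400 mg plus 7 suspended days would give 8000/27 = 296.3 mg, absent, although every dosed day was above the limit.

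**4. Sensitivity of the discontinued-versus-continued tabulation, if overdose is part of it.** The sample-size rationale (protocol 7.5.2) presumes 20% hepatic toxicity in 200 patients, so 40 patients. Pooling the three cited studies, 1 + 2 + 2 = 5 of 47 + 11 + 4 = 62 such patients discontinued (8.1%). That gives 40 × 5/62 = 3.2 discontinued and 36.8 continued. One misclassified continuing patient moves that group's overdose share by 100/36.8 = 2.7 points. With discontinuation at 1/47 there are 39.1 continuing patients and the step is 2.6 points; at 2/4 there are 20 and it is 5.0 points. How many patients would be misclassified cannot be derived from the documents.

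**The case against.** The footnote's last clause could be read as covering any single administration above the limit. On that reading the classification is right and only the wording is at fault. But the sentence names the initial and mean doses as the quantities to calculate, and under the alternative the mean would have no role. The mean-based reading is the natural one, and the text needs correcting on either.

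The consequence is small, and this stands. Overdose is one descriptive line. It is not a subgroup factor in SAP 5.4, so no risk ratio or risk difference is planned for it. First-day and mean maintenance dose are tabulated directly. Investigators report overdoses whether or not an adverse event occurred (protocol 9.1 and 9.4.3), and treatment status is listed by patient (SAP 9). These outputs preserve the information but do not correct the tabulated flag.

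A reader might infer that the SAP contradicts itself, because its analysis of concomitant medications leaves out drugs started after the last onset of the event while the Vfend dose has no such cut-off. The documents do not support that. The cut-off belongs to a different analysis, and the discontinued-versus-continued tabulation states no onset cut-off for either item.

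A reader might also infer that any dose cut after a reaction clears the flag. It cannot clear one set by the initial dose, and dilution works only within a route, because injection and oral means are kept separate.

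**Conclusion.** The point holds. Footnote 3 states a rule that, read naturally, gives the wrong classification for a patient whose initial dose is within its limit but who is above the ceiling on a substantial share of maintenance days. In the assumed histories that share can reach 25% to 75%, depending on the two doses; it is 0% if the remaining days sit at the limit. A later cut or increase within the same route can change the flag.

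The formula is exact, but the doses are assumptions. The documents give no dose distribution, so neither the number of patients affected nor the error in the overdose count can be estimated.

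The tempting stronger reading is that the hepatic and visual event comparison is biased in a known direction. The documents do not support it. SAP 8.2.3.1 does not name overdose within status of administration, so the flag may not enter that comparison. If it does, a cut can turn it off in a continuing patient or in one who later discontinues, and an increase can turn it on. The net direction is unknown.

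The correction is worth making because the rule misclassifies, the data are already collected and the cost is low. No endpoint or planned risk-ratio analysis is affected.

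**What to change.** Reword footnote 3 so that overdose is present when the dose on any recorded day exceeds the limit for the patient's age, weight and route. Compare Day 1 with the Day 1 limit and later days with the limit from Day 2. For oral dosing, compare the daily total with twice the per-dose limit (600 mg a day from Day 2 for an adult of 40 kg or more), because the adult and under-50 kg child oral ceilings are worded as total daily dosage. Report the number of days above the limit. Keep mean maintenance dose as a descriptive line and say whether suspended days enter it. If overdose is used in the discontinued-versus-continued tabulation, also show it using doses up to event onset only.

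As a side point, any overdose rule must state the limit used where the dosing text gives no numeric maximum, notably intravenous dosing in children aged 2 to under 12, or 12 and over and under 50 kg.

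The cost is SAP wording and reprogramming. Dosage form, dose, frequency, period and calculation weight are already collected under protocol 7.3.2. The downside is a slightly higher count that may include isolated rounded or mistranscribed doses; the days-above-limit line makes these visible.
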